# **ABREVIATIONS LIST**

INS -- Institut National du Sport

PTVS - Post Traumatic Visual Syndrome

# Rationale and study purpose

Concussion is a mild form of traumatic brain injury that affects 1.6 to 3.8 million people each year in the United States [1]. However, the exact incidence is difficult to determine due to underreporting by patients [2]. Concussion is defined as a set of pathological reactions leading to direct damage of the brain, which may occur from a direct or indirect blow to the head [3]. Common symptoms fall in three domains: (1) physical signs and symptoms (e.g. headache, dizziness, nausea, balance problems, fatigue, light and noise sensitivity), (2) cognitive deficits (e.g. difficulty concentrating, decreased reaction time, memory problems), and (3) emotional reactions (e.g. depression, anxiety) [4, 5]. Visual complaints, such as blurred vision, eye fatigue, and difficulties sustaining attention, are particularly common in adult concussions [4, 6]. Recently, we have witnessed a shift in the focus of some research on concussion to include more detailed investigation of vestibular and visual symptoms [2].

One common visual deficiency that can mimic symptoms of concussion is convergence insufficiency. Convergence insufficiency (CI) is a common binocular vision disorder [7] often associated with a wide range of symptoms including headaches, poor concentration, slow reading, blurred vision, diplopia, and eyestrain [8-10]. Various treatment options are commonly prescribed such as home-based therapy, pencil push-ups, office-based vision therapy, and orthoptic treatment [11]. Orthoptic exercises have been in use for over 70 years and represent an established therapy for CI [12]. Despite frequent use, the effectiveness of these treatments had not been examined until recently by the Convergence Insufficiency Treatment Trial (CITT) group which compared the effectiveness of different treatment methods on CI. It was determined that orthoptic exercises resulted in significantly greater improvement of symptoms in children aged 9 to 17 years as compared to other common treatments [11].

To date, tests for CI and other orthoptic visual dysfunctions have yet to be validated or tested for reliability in healthy adults. Reliability is an important measurement property for all measures of health [13]. The Consensus-based Standards for the Selection of Health Measurements Instruments (COSMIN) has defined reliability as "the extent to which scores for patients who have not changed are the same for repeated measurement under several conditions". There are several types of reliability that are of interest in measurement of health outcomes, such as interrater reliability, intra-rater reliability, internal consistency, and test-retest reliability. In terms of health measures, such as the orthoptic tests, they must be valid and sensitive to the system of interest (i.e. visual system) in order to be used clinically to guide patient management. Presently, it is difficult to quantify the validity of these orthoptic measures due to a lack of a "gold-standard" in this domain [14], thus, test-retest reliability must be established [15]. Therefore, the purpose of this research is to determine the test-retest reliability of seven orthoptic measures across two independent measurements. As these tests have applicability in many health conditions (e.g. concussion, etc), this study has the potential to contribute to improved management of symptoms related to the visual system.

# Study design and methods

The overall study design is a test-retest reliability study of seven different orthoptic tests in healthy participants aged 16 to 35 years. In order to determine if there is clinically useful agreement and consistency between the results when the orthoptic tests are repeated, each participant will be assessed at two time points.

At each time point, participants will be evaluated with seven orthoptic measures:

- (T1) at participant's earliest convenience
- (T2) 1 week following their initial visit

Each of the seven orthoptic measures will be administered to each participant by the same clinician (DT). To minimize the risk that the clinician will remember the scores of any participant, we will set up each testing day so that the clinician sees up to five participants in a random order. At their next and final visit, all the same participants will return to be evaluated, but their order will be altered from their initial visit. To further decrease the likelihood of clinician memory affecting the responses, a research assistant will record the test results as reported verbally by the clinician. After a participant has completed his/her two visits, a research assistant will enter the data into the proprietary software which will provide the clinician with their official "chart" that is required as part of good management practice.

Test-retest reliability studies have used varying durations between testing intervals ranging from consecutive days to a few weeks [15, 16]. We have selected a seven-day interval between testing times because of scheduling efficiency and potential carry-over effects of the orthoptic tests. First, although these orthoptic measures are standard tests that have been used in the public, certain individuals may experience mild symptoms that typically resolve in minutes to a few hours. Therefore, if we repeated the test within a few hours, this may lead to inaccurate measurements due to residual effects of the test, itself. Although we could conduct the second test within 24 to 48 hours, we are concerned that scheduling might be difficult as participants may only have free time at particular times/days of the week (e.g. each Monday afternoon). Thus, we have chosen to have the tests repeated exactly seven days later. Finally, the time interval must be one in which it is unlikely that a participant may change. For instance, with an interval that is too long (e.g. one month) there is an increase likelihood of the participant having changed significantly from his/her initial measurement. We believe a one week interval is short enough that participants are very unlikely to change unless a major event occurs (e.g. car accident). Therefore, we believe a one-week interval represents the appropriate balance for avoiding a carry-over effect, probability of change in the participant, and feasibility.

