#### *Saccadic movements or oculomotor capacity: (Score = bad, medium, good)*

A light appears on the screen and the participant move their eyes to fix on the object. While they eyes adjust, they will temporarily cover small distances until they achieve a fixed focus. These are called saccadic movements. Lights appear and disappear, in different locations on the screen, at a rate of 100 per minute, lasting 2 minutes. The test result is scored by the evaluator based on a global impression over the entire 2 minutes, with 3 separate sub scores on an ordinal scale for quality (bad, medium, good), for synchronization (bad, medium, good) and saccadic correction (many corrections, few corrections, no corrections). The three sub scores are combined into an overall score according to our industry partner's (Apexk) proprietary algorithm.

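### The delayed chart stops the clinician looking up first-visit scores but not recalling them, so ICCs for the clinician-judged tests may be too high

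*Combined protocol and SAP*

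**What the plan says.** The protocol's purpose (Rationale and study purpose) is to "determine the test-retest reliability of seven orthoptic measures across two independent measurements". Study design and methods then sets out how the two measurements are taken:

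- One rater: "Each of the seven orthoptic measures will be administered to each participant by the same clinician".
- The threat is named, and the aim is to reduce it: "To minimize the risk that the clinician will remember the scores of any participant".
- On each testing day "the clinician sees up to five participants in a random order".
- At the second visit, seven days later, "all the same participants will return to be evaluated, but their order will be altered from their initial visit".
- Recording: "a research assistant will record the test results as reported verbally by the clinician".
- Chart: "After a participant has completed his/her two visits, a research assistant will enter the data into the proprietary software", and only then does the clinician receive the official chart.

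Data collection and analysis keeps the clinician out of data extraction and analysis, but this does not affect how the second measurement is made. No masked reading, second rater or check on recall is described. Among the tests, the saccadic result is "scored by the evaluator based on a global impression over the entire 2 minutes".

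**The concern.** To report a score aloud, the clinician must first know it. Handing the pen to an assistant removes the written record from the clinician's hands but not the value from the clinician's mind. Changing the order does not hide who is in the chair, and because the whole group returns together, the clinician knows that each session that day is a retest.

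Exact recall is not needed for bias. A general impression, such as weak convergence or good saccades, can shift a borderline endpoint towards the first result. That shrinks within-person differences, so the error runs one way: the primary ICC rises and the Bland-Altman limits narrow. Both make a test look more reliable than it is. The results are meant to support a larger project in people with concussion symptoms, so estimates that are too favourable would carry forward.

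**Working it through.** **The plan's own figure.** Sample Size Calculation gives a precision of ±0.20 with 20 participants, two measurements each and a true ICC of 0.75. Bonett's formula with full interval width 0.40 gives

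n = 8 × 1.96² × (1 − 0.75)² × (1 + 0.75)² / (2 × 0.40²) + 1 = 8 × 3.8416 × 0.0625 × 3.0625 / 0.32 + 1 = 19.4, rounded up to 20.

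The figure reproduces (half-width 0.197 at n = 20). It concerns random error only. Recall is a bias, and more participants would not remove it.

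**Which tests are exposed.** From the descriptions under Orthoptic Measures of the Visual System:

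| Test | What fixes the score | Exposure to recall |
|---|---|---|
| Saccadic movements | Clinician's overall impression on three three-level sub scores, then an algorithm | Highest |
| Anatomic deviation (3 m, 30 cm) | Prism that cancels a movement the orthoptist sees | High |
| Motor punctum proximum | Point where the eyes stop converging symmetrically; the protocol does not say who calls it, and I take it to be the clinician | High |
| Fusion with convergence and with divergence | Largest prism the participant can accommodate; the clinician knows the prism | Lower, but not masked |
| Fusional proximum | Participant starts to see double | Low |
| Stereoscopic acuity | Last object the participant identifies | Low |

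**Size, as an illustration.** The documents give no amount of recall and no expected ICC below 0.75. I assume a pull w of 0.1 to 0.3 and a true ICC r = 0.60. Let recorded T2 = (1 − w) × unbiased T2 + w × T1, with unit variances and equal means. Then:

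- covariance = w + (1 − w)r
- variance of recorded T2 = (1 − w)² + w² + 2w(1 − w)r
- ICC = covariance / mean of the two variances, which matches the Analysis plan's between-person share of total variance
- T1 − recorded T2 = (1 − w)(T1 − unbiased T2), so the limits of agreement narrow by the factor 1 − w

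| w | Covariance | Variance of T2 | ICC | Width of limits |
|---|---|---|---|---|
| 0 | 0.600 | 1.000 | 0.60 | 1.0 |
| 0.1 | 0.640 | 0.928 | 0.640 / 0.964 = 0.66 | 0.9 |
| 0.2 | 0.680 | 0.872 | 0.680 / 0.936 = 0.73 | 0.8 |
| 0.3 | 0.720 | 0.832 | 0.720 / 0.916 = 0.79 | 0.7 |

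**If only some participants are affected.** Suppose half are pulled and half are not. At w = 0.2 the covariance is (0.680 + 0.600)/2 = 0.640, the T2 variance is (0.872 + 1)/2 = 0.936, and the ICC is 0.640 / 0.968 = 0.66. At w = 0.3 the same steps give 0.660 / 0.958 = 0.69.

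**In studies of this size.** In 40,000 simulated studies of 20 people with a true ICC of 0.60 and every participant pulled, an observed ICC of at least 0.75 occurred in 11% with no pull, and in 23%, 41% and 65% at w = 0.1, 0.2 and 0.3.

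**The case against.** The plan has a fair defence, and much of it stands.

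- It undertakes to minimise the risk, not to abolish it. Its reference to independent measurements can be read simply as two separate occasions; it does not promise masking.
- Withholding the chart until both visits are done is a genuine safeguard. With the assistant keeping the record, the clinician has no evident way to look up the first result.
- The recall task is heavy. Each person yields about 12 values (stereoscopic acuity 1, motor punctum 1, convergence fusion 2, saccadic sub scores 3, deviation 2, fusional proximum 1, divergence fusion 2), so five people yield about 60, voiced once and a week old. This makes exact recall unlikely. It does not exclude a remembered impression.
- Using one rater is legitimate in test-retest work, and a second is not needed to answer this point.
- The model is crude. It assumes perfect memory of T1 and the same pull on everyone, and a linear blend does not describe three-level ratings.

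A reader might infer that all seven tests are compromised. The documents do not support that: double vision and stereoscopic acuity are the participant's own percepts, and the fusion tests rest on what the participant can accommodate. A reader might also infer that recall would carry tests over a pass mark of 0.75. The plan treats 0.75 as a clinically relevant planning value and 0.5 as the lower bound of acceptability, but states no rule by which a test is declared reliable.

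**Conclusion.** The concern holds in limited form. The safeguards prevent look-up and may weaken recall, but they do not mask the second visit. For the motor punctum proximum, the cover/prism deviation and the saccadic ratings, the second score can drift towards the first, and any such drift raises the ICC and narrows the limits of agreement.

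The documents do not show that drift will occur, or how large it would be. The rise from 0.60 to between 0.66 and 0.79 depends on an assumed starting ICC and an assumed pull of 0.1 to 0.3 on every participant; with half affected at 0.2 to 0.3 it is 0.66 to 0.69. These figures show that modest recall could matter. They do not estimate the bias in this study, and they leave the sample size calculation untouched.

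**What to change.** In Study design and methods, replace the rule that the clinician voices each result with a procedure for each type of test:

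- **Both punctum proximum tests.** The endpoint is called by the clinician for the motor test and by the participant's report of double vision for the fusional test. The research assistant already recording the results reads the distance in cm from a scale the clinician cannot see, and does not announce it. (The fusional test's heading gives diopters while its text gives cm; this assumes cm.)
- **Stereoscopic acuity.** The assistant records the last object the participant identifies.
- **Prism and saccadic tests.** The clinician necessarily knows these values, so leaving a prism number unspoken would hide nothing. State that the second visit is not masked to the first, and interpret these ICCs as possible upper estimates.

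This needs no extra staff, visit or test. The costs are brief training, possible reading error by the assistant and slightly longer sessions. Masking of the distance tests stays partial, because the clinician can still see roughly where the object stops. For the saccadic and deviation tests, where exposure is greatest, the remedy is disclosure only.

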### Orthoptic Measures of the Visual System

Most clinicians understand that eye function can be tested for acuity, field of vision and convergence using standard tests available at any clinician's office. However, these tests can only detect gross deficiencies. Optometrists have access to specialized equipment to detect more subtle visual deficiencies. The field of orthoptics uses even more advanced equipment to measure very small deviations in several domains of the visual system. All orthotic measures will be conducted by a single clinician. A detailed description of the 7 orthoptic measures follows:

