### Data collection and analysis

At the point of recruitment, a research assistant will describe what is needed of the participant in the study and then the participant will provide informed consent. At the first visit, a research assistant will collect demographic information of each participant. At each visit, the seven orthoptic tests will be administered to the participant by the single clinician (DT) as outlined above. Once each participant has completed their two testing periods, the data will be entered into the patient file by a research assistant. Following, the data will be exported into a comma-separated file for analysis using statistical software. The clinician conducting the orthoptic tests will not be involved in the data extraction or analysis phases.

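### Chart release is tied to each participant's second visit, not to the end of testing, so the only rater could see completed test-retest results before retesting others

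*Combined protocol and SAP*

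**What the plan says.** Study design and methods sets the trigger for the chart: "After a participant has completed his/her two visits, a research assistant will enter the data into the proprietary software which will provide the clinician" and continues "with their official 'chart' that is required as part of good management practice". Data collection and analysis gives similar timing for data entry: "Once each participant has completed their two testing periods, the data will be entered into the patient file by a research assistant". It also keeps the rater away from later steps: "The clinician conducting the orthoptic tests will not be involved in the data extraction or analysis phases".

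On who measures, Orthoptic Measures of the Visual System states: "All orthotic measures will be conducted by a single clinician". On scheduling, Study design and methods states "we will set up each testing day so that the clinician sees up to five participants in a random order" and, for the interval, "Thus, we have chosen to have the tests repeated exactly seven days later". First visits are set at each participant's convenience, with no common start date.

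The same section has safeguards against the clinician remembering scores. The order of participants is changed at the second visit, and an assistant writes down results that the clinician calls out. No section says that charts are withheld until the last participant has been retested.

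**The concern.** The stated safeguards deal with one risk: that the clinician recalls a participant's first score when taking the second. They do not deal with information passing from finished participants to those still to be tested. The bar on extraction and analysis does not cover the chart, which comes from a separate step.

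A rater who sees how far their own first and second readings differ may change technique or scoring criterion part-way through. Two tests leave clear room for this. The saccade sub-scores are global impressions on three-level scales, and the anatomic deviation is the prism at which the orthoptist no longer sees movement. If the criterion moved, early and late pairs would not describe the same measurement process. The ICC (the primary outcome) and the limits of agreement would then mix the two. Rationale and study purpose states the aim as reliability over two independent measurements, and that independence is what would be weakened.

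**Working it through.** **Inputs.** 20 participants and an assumed true ICC of 0.75 (Sample Size Calculation). At most five participants per testing day, a retest after seven days and a chart after each participant's second visit (Study design and methods). One rater (Orthoptic Measures of the Visual System).

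**The plan's own figure.** The large-sample half-width for an ICC r from k measurements on n participants is 1.96 × √[2(1−r)²(1+(k−1)r)² / (k(k−1)(n−1))]. With r = 0.75, k = 2 and n = 20 this is 1.96 × √[2 × 0.0625 × 3.0625 / 38] = 1.96 × 0.1004 = 0.197. The stated ±0.20 is reproduced and is not in dispute.

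**Exposure.** The number of groups is at least 20/5 = 4. Each group has its own testing day and returns seven days later, so there are also at least four retest days. Two schedules bracket what the text allows, taking full groups of five:

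- *Compact:* four first-visit days in one week and four retest days in the next. All first visits precede any completed pair. The first group's pairs are complete before the retests of the other 20 − 5 = 15. Those 15 have only their second measurement after that point.
- *Sequential:* each group finishes before the next begins. The same 15 of 20 (75%) have both measurements after the first pairs are complete.

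Under either schedule, prompt charting would let the rater see completed pairs before 15 retests.

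**Direction.** Agreement could look better or worse.

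- *Better:* suppose feedback multiplies the within-person SD by a factor c wherever it can act. This is an assumption; the documents give no figure. Take between-person variance 0.75 and within-person variance 0.25.
  - Sequential: ICC = 0.75 / [0.75 + 0.25(0.25 + 0.75c²)], which is 0.778 for c = 0.9 and 0.829 for c = 0.7.
  - Compact, where only the second reading is affected: replace c² by (1 + c²)/2. The results are 0.764 and 0.788.
- *Worse:* if the criterion moves by d between a participant's two visits, the expected within-pair variance rises by d²/2, and the ICC as defined in the Analysis plan falls. The compact schedule puts any change in exactly that place for the 15.

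The sign and size of the result therefore come from the schedule and from the chosen c or d. The documents fix none of these. The figures show only this dependence and are not an expected shift.

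**The case against.** The strongest case against is that nothing shows the feedback would happen. The text says only that entry follows the second visit. It does not say how soon the chart arrives, or that it sets the two visits side by side. The timing sentence in Data collection and analysis can also be read as entry after everyone has finished, and it mentions no chart for the clinician. All of this stands, and it limits the point to an open path.

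The clinician also called out every score, so a chart would add at most the pairing, and only for participants already finished. It cannot affect those participants' own pairs. This stands too, but the safeguards assume that the clinician does not retain those scores, and a chart could restore them in writing.

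Several endpoints depend on the participant: stereoscopic acuity on the last object identified, the fusional proximum on when double vision begins, and the fusion tests on the largest prism tolerated. Clear rater judgement is documented mainly for saccades and anatomic deviation, so the point should not be spread evenly over all seven tests.

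A reader might infer that later pairs will agree better than in routine use and that the ICC will be inflated. The documents do not support this. The direction is open, and the plan describes the chart as part of ordinary good practice, so routine raters may well see such results themselves.

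**Conclusion.** The point holds as a gap in the masking rule. The chart is triggered participant by participant, there is one rater, and no rule delays release to the end of testing. With full groups of five, 15 of 20 participants have at least their retest after the first pairs are complete. That count follows from the plan's own figures. Actual exposure also needs prompt delivery and a chart showing both visits, and the documents state neither.

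It would go too far to say that the clinician will receive paired results during testing, or to quote an ICC shift as expected. Any shift would be a bias, which the ±0.20 does not include, and with 20 participants it would be hard to detect afterwards. That favours preventing it. The weight is minor: a cheap improvement, not the correction of a demonstrated error.

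**What to change.** In Study design and methods, state that charts are released to the clinician only after the last participant's second visit, and that any earlier release for a clinical need is logged with its date. In Data collection and analysis, state that the assistant may enter data earlier only if the clinician has no access to the file.

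The cost is about one sentence in each section, and the charts of healthy volunteers reach the clinician somewhat later. The plan already accepts a delay of this kind by entering first-visit results only after the second visit. Sample size, schedule and tests do not change.
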